9.3.4 Pharmacokinetic Analyses

Analyses will be carried out on the PK analysis population. All PK parameters will be presented by listings and descriptive summary statistics (mean, standard deviation, coefficient of variation, median, minimum, and maximum) separately by treatment group.

Individual and mean serum RO7121661, RO7247669, and nivolumab versus time data will be tabulated and plotted by treatment group. Graphical displays of PK data may also be provided. The serum pharmacokinetics of RO7121661, RO7247669 and nivolumab will be summarized by estimating total exposure (area under the curve), maximum concentration, total clearance, volume of distribution at steady-state, and terminal half-life, as appropriate for the data collected. Estimates for these parameters will be tabulated and summarized. Inter-participant variability and drug accumulation will be evaluated.

9.3.5 Immunogenicity Analyses

The immunogenicity analyses will include all participants with at least one ADA assessment, irrespective of whether or not the participant receives any treatment ([Shankar et al., 2014](#)).

The numbers and proportions of ADA-positive participants and ADA-negative participants at baseline (baseline prevalence) and after study drug administration (post-baseline incidence during both the treatment and follow-up periods) will be summarized.

- Participants are considered to be ADA positive if they are ADA negative at baseline but develop an ADA response following study drug administration (treatment-induced ADA response), or if they are ADA positive at baseline and the titer of one or more post-baseline samples is greater than the titer of the baseline sample by a scientifically reasonable margin such as at least 4-fold (treatment-enhanced ADA response).
- Participants are considered to be ADA negative if they are ADA negative at baseline and all post-baseline samples are negative, or if they are ADA positive at baseline but do not have any post-baseline samples with a titer that is greater than the titer of the baseline sample by a scientifically reasonable margin such as at least 4-fold (treatment unaffected).

The relationship between ADA status and safety, efficacy, PK, and biomarker endpoints may be analyzed and reported descriptively via subgroup analyses.

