9.2 POPULATIONS FOR ANALYSES

For purposes of analysis, the following populations are defined in [Table 8](#).

Table 8 Analysis Populations

Population	Description
Intent-to-treat	All randomized participants will be included in the intent-to-treat population.
Safety	All participants randomized to study treatment and who received any amount of the study treatment, whether prematurely withdrawn from the study or not, will be included in the safety analysis.
Pharmacokinetic	All participants who have received at least one dose of study treatment and who have data from at least one post-dose sample will be included in the PK analysis population. Participants will be excluded from the PK analysis population if they significantly violate the inclusion or exclusion criteria, deviate significantly from the protocol, or if data are unavailable or incomplete which may influence the PK analysis. Excluded cases will be documented together with the reason for exclusion. All decisions on exclusions from the analysis will be made prior to database closure.
Immunogenicity	Participants who had at least one pre-dose or at least one post-dose ADA assessment will be included and analyzed according to the treatment they actually received or were allocated to receive. The relationship between ADA status and safety, efficacy, PK, and biomarker endpoints will be analyzed and reported descriptively via subgroup analyses.
PRO-evaluable population	All randomized participants with a non-missing baseline assessment and at least one post-baseline assessment for the respective PRO will be included in the PRO-evaluable population.

ADA = Anti-drug antibody; PK = Pharmacokinetic; PRO = Patient-reported outcome.

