9.3.6 Pharmacodynamic Analyses

All PD parameters will be presented by listings and descriptive summary statistics separately by treatment group.

All analyses of PD and exploratory biomarkers will be based on the safety analysis population (Section [9.2](#)).

For the analysis of PD biomarkers, the primary evaluation will be based on the observed change from baseline. Both actual values and estimated parameters will be presented in summary tables and graphically as deemed appropriate.

To assess predictability of a biomarker, the association between clinical outcome and the biomarker level or changes thereof will be explored.

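### Relating ever/never ADA status to OS and PFS by plain subgroups favours ADA-positive participants through immortal time; the ADA incidence denominator is also left open

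*Combined protocol and SAP*

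**What the plan says.** **Who is included.** Table 8 (section 9.2) states: "Participants who had at least one pre-dose or at least one post-dose ADA assessment will be included". They are "analyzed according to the treatment they actually received or were allocated to receive". Section 9.3.5 is equally wide: "all participants with at least one ADA assessment, irrespective of whether or not the participant receives any treatment". One sample is enough, a pre-dose sample counts, and no dose is needed.

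**How status is set.** Under section 9.3.5 a participant is positive if "ADA negative at baseline but develop an ADA response following study drug administration (treatment-induced ADA response"), or if a positive baseline titer rises by a margin such as 4-fold. A participant is negative if "ADA negative at baseline and all post-baseline samples are negative", or if positive at baseline with no later sample showing such a rise. Neither negative rule sets a minimum number of post-baseline samples. All of these rules start from a baseline result.

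**What is reported.** Section 9.3.5 asks for positives and negatives at baseline and "after study drug administration (post-baseline incidence during both the treatment and follow-up periods) will be summarized". It gives the incidence no denominator of its own.

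**Link to efficacy.** Table 8 says: "The relationship between ADA status and safety, efficacy, PK, and biomarker endpoints will be analyzed and reported descriptively via subgroup analyses". Section 9.3.5 repeats the sentence but makes it optional. Neither place names a landmark or a time-dependent method.

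**Standing.** In Table 5, ADA incidence is a secondary endpoint for RO7247669 and nivolumab. The relationship between ADA status and efficacy is exploratory.

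**The concern.** ADA-positive status can arise only after the first dose and can be seen only at a scheduled draw. OS and PFS start at randomization. Anyone who ends up in the ever-positive group has, by construction, survived up to the draw that turned positive, while anyone who dies or stops sampling first stays in the never-positive group. The positives are credited with time in which they could not have died as positives.

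Section 8.6 itself warns that ADAs may reduce efficacy. A method that leans towards better survival in ADA-positives leans against detecting that for a new bispecific antibody. Calling the comparison descriptive does not take the bias out of a pair of Kaplan-Meier curves.

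The second, smaller matter is the incidence. Read literally, the negative rules are met by a participant with no post-baseline sample at all. A participant with a post-dose sample but no baseline sample is in the population yet fits neither definition.

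**Working it through.** The documents give no expected ADA incidence and no ADA effect, so there is no planned figure to reproduce. The size below is an illustration.

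**Inputs from the documents**
- Median OS on PD1 inhibitors in second line: 8.3 to 10.9 months (section 2.3).
- First dose on the day of randomization or the next day (section 6.3.1).
- ADA draws: pre-dose at Cycles 1 to 5, at Cycle 7 and every 3 cycles after that, and at the discontinuation visit (Table 2). With 14-day cycles the first scheduled post-baseline draw is about day 14, and C5D1 is 4 × 14 = 56 days after the first dose.

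**Assumptions**
- Exponential OS, censored at 24 months.
- Median time to treatment stop 2 or 4 months; discontinuation sample 0.5 month after the last dose.
- 20% or 40% of participants prone to ADA; median onset 0.5, 1, 2 or 4 months.
- No effect of ADA on OS.

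This gives 2 × 2 × 2 × 4 = 32 scenarios, each with 400,000 simulated participants.

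**Step 1: ever/never comparison.** Ratio = (deaths ÷ person-time from randomization in ever-positives) ÷ (the same in never-positives). The true value is 1. Selected scenarios:

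| Median OS (mo) | Median treatment (mo) | Median ADA onset (mo) | ADA-prone | Ever/never ratio | Negatives with a post-baseline sample only | Median OS, pos. v neg. (mo) | Day-56 landmark |
|---|---|---|---|---|---|---|---|
| 8.3 | 2 | 0.5 | 20% | 0.91 | 0.96 | 9.1 v 8.1 | 1.01 |
| 8.3 | 4 | 1 | 40% | 0.83 | 0.88 | 9.8 v 7.6 | 0.99 |
| 8.3 | 4 | 4 | 40% | 0.74 | 0.79 | 11.2 v 7.6 | 1.00 |
| 10.9 | 4 | 0.5 | 20% | 0.91 | 0.96 | 11.8 v 10.7 | 1.00 |
| 10.9 | 4 | 2 | 20% | 0.83 | 0.87 | 13.1 v 10.5 | 1.01 |
| 10.9 | 4 | 4 | 40% | 0.76 | 0.79 | 14.0 v 10.2 | 0.99 |

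Over all 32 scenarios the ever/never ratio is 0.74 to 0.91, and the bias grows as onset is later. Restricting the negatives to participants with a post-baseline sample leaves 0.79 to 0.96, so cleaning up the denominator does not remove it. The landmark gives 0.99 to 1.01 throughout. PFS was not simulated; the direction follows from the same mechanism.

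**Step 2: what could be hidden.** If the bias roughly multiplies a true ratio, a harmful ADA effect of 1/0.91 = 1.10 to 1/0.74 = 1.35 would show as about 1.

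**Step 3: incidence.** Let f be the share without a post-baseline sample and p the incidence among the rest. If that share is counted as negative, the reported incidence is p × (1 − f).
- Death before day 14: f = 1 − 2^(−(14/30.44)/median OS), which is 3.8% at 8.3 months and 2.9% at 10.9 months.
- In the simulation, f was 3.0% to 4.1%.
- An assumed p of 24% gives 0.24 × 0.97 = 23.3% or 0.24 × 0.96 = 23.0%.

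**The case against.** The strongest reply is that the ADA-efficacy comparison is exploratory and descriptive, and optional in section 9.3.5. No ADA hazard ratio, test or decision rule is planned. The term subgroup analyses does not exclude a landmark definition, and section 9.3 defers detail to a separate technical document that is not available here. This limits the consequence but does not answer the point: status defined by post-dose events and compared by subgroup is biased unless its timing is handled, and nothing in the plan handles it.

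Four stronger readings are tempting, and the documents do not support them.
- **That incidence does count untreated and baseline-only participants.** This is a literal reading of the negative rules. The text does not say so, and its reference to incidence after study drug administration points the other way. The denominator is unstated rather than shown to be wrong. Never-treated participants with a sample should also be very few: Table 2 draws the first ADA sample within 4 hours before the first infusion, and dosing follows randomization within a day.
- **That the arm comparison is distorted.** No between-arm ADA contrast is planned, and nothing in the documents shows different early dropout by arm.
- **That section 9.3.6 has the same fault.** It says only that the "association between clinical outcome and the biomarker level or changes thereof will be explored". It names no subgroup method, so the point does not carry over.
- **That ADA-positives will look better.** That is the direction of the bias. A true harmful effect could offset it, so the observed result could go either way.

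**Conclusion.** The concern holds for the ADA-efficacy comparison. Ever/never ADA subgroups for OS and PFS carry immortal-time bias in favour of ADA-positives. The spurious OS ratio is about 0.74 to 0.91, conditional on assumed treatment duration, ADA onset and ADA frequency; only the OS range and the sampling schedule come from the documents. The result at risk is exploratory. The primary OS comparison of RO7247669 with nivolumab is by randomized arm and is not touched.

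The incidence denominator is a secondary matter of definition, worth about one percentage point at an assumed 24%. It still deserves a sentence because incidence is a secondary endpoint. Table 8 already shows how to write it: the PK population requires a dose and a post-dose sample, and the PRO-evaluable population requires both a baseline and a post-baseline assessment.

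**What to change.** - **ADA and efficacy.** Relate ADA to OS and PFS with ADA status as a time-dependent covariate. Alternatively, use a landmark, for example status by C5D1 among participants still at risk, with follow-up counted from the landmark.
- **Incidence and prevalence.** Report incidence among treated participants with at least one post-baseline ADA result, and prevalence among those with a baseline result. Show participants with a missing baseline separately and class the rest as not evaluable.
- **Consistency.** Make Table 8 and section 9.3.5 agree on whether the ADA-efficacy analysis is planned or optional. Also reconcile the incidence that section 9.3.5 reports for the follow-up period with Table 2, which schedules no ADA draw after the discontinuation visit.

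**Cost.** The cost is wording in section 9.3.5, Table 8 and the analysis plan, with no new data. A landmark has two drawbacks. It drops participants who fail before it, and it classes later seroconverters as negative. If onset were uniform over months 0.5 to 4 (an assumption), a day-28 landmark would capture (0.92 − 0.5)/3.5 = 12% of onsets and a day-56 landmark (1.84 − 0.5)/3.5 = 38%. The time-dependent covariate avoids both and is the better default.

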1.3 SCHEDULE OF ACTIVITIES

The schedule of activities are provided in [Table 1](#), [Table 2](#), and [Table 3](#).

Table 1 Schedule of Activities

Protocol Section	Cycle length 14 days	Screening	On dosing days of all treatment Cycles ^a	Cycle 1 - 5 Day 8	Treatment Discontinuation	Follow-up	In case of Grade ≥2 IRR, suspected anaphylaxis, or Grade ≥ 2 suspected imAEs	
	Day (D)	D -28 to D -1 (unless otherwise indicated)	Every 14 Days (-1/+3 days)	(± 1 day)	≤ 30 Days after Last Dose	90 (±7 days) post last dose, then every 3 months (±2 weeks)	At the time of event	≥48 hours after the onset of an IRR
Screening Assessments								
	Informed consent (incl. RBR)	x						
8.2.8	Medical history and demography	x						
8.2.5	Royal Marsden Risk Score	x						
IMP Administration								
6.1	Study drug administration		x					
Clinical Assessments								
6.5	Previous and concomitant treatments	continuous					x	x
8.3	Adverse events					x	x	x
8.2.1	Physical examination	x	x		x		Weight only	
8.2.1	Height	x						
8.2.2	Vital signs ^b	x	x		x			
8.2.3	12-lead ECG	x	x		x		x	
8.2.4	ECOG performance status	x	x		x			
8.2.6	TTE or MUGA	x						
8.1.2	PRO-assessments	Refer to the PRO assessments table for specific Timepoint Details						
8.8.2	Nutritional assessment (optional)		C1, C4 and upon occurrence of colitis					
8.1.1	Tumor assessment (CT scan of chest, abdomen, pelvis, brain, and other regions as clinically indicated)							
8.11.4	Post-study survival and anti-cancer therapies					x		
Local Laboratory Assessments								
8.2.7 and Appendix 4	Viral serology	x						
	Quantitative immunoglobulins	x						
	Hematology	x	x		x		x	
	Blood chemistry	x	x		x		x	
	Coagulation	x	x		x		x	
	Lipid panel	x	C1 and then every 4 cycles		x			
	Thyroid function	x	C3 and then every 3 cycles					
	Auto-antibody panel	x	In case of suspected Grade ≥ 2 imAEs				In case of suspected imAEs	
	Urinalysis	x	x		x			
	IgE/tryptase						x ^d	x ^d
	Pregnancy test	x (blood test, D -7 to D -1)	C2 and then every 4 weeks (blood or urine)		x (blood or urine)	x ^e (5 months after the last dose)		
Central Laboratory Assessments								
8.5	PK	Refer to Hourly Schedule of Assessments for specific sample collection timepoint details					x	
8.6	ADA							
8.8.1	PD plasma						x	
	PD serum						x	
	PD whole blood flow cytometry						x	
	Whole Blood RNA							
	bTMB/ctDNA							
8.7.1	WGS							
8.8.1	Archival tumor sample							
8.8.2	Fresh tumor biopsy (optional)							
	Tongue scrape (optional)							

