- d) Tryptase and total IgE should be analyzed for participants who experience a Grade \geq 3 IRR during the first study treatment administration or for participants who experience a Grade \geq 2 IRR for the first time with the second or subsequent study drug infusion or with clinical signs of hypersensitivity reaction at any time of the conduct of the study. A second sample for IgE/tryptase analysis should be collected at least 48 hours after the onset of the reaction to rule out the possibility of an anaphylactic reaction.
- e) An at-home pregnancy test will be provided. The test has to be conducted 5 months after the final dose (for women of childbearing potential), and the site will inquire about the result during the second follow up.

Table 2 Hourly Schedule of Assessments

	Q2W regimen; Cycle length 14 days	Screening	Cycle 1				Cycle 2			Cycle 3		Cycle 4		Cycle 5				Subsequent Cycles		Treatment Discontinuation
	Day		Day 1				Day 1			Day 1		Day 1		Day 1				Day 1		
	Scheduled Time (h) ^a		PreDose	EOI	4	168	PreDose	EOI	4	PreDose	EOI	PreDose	EOI	PreDose	EOI	4	168	PreDose	EOI	At Visit
Protocol Section	Time Window		-4h	+ 10 min	+/- 1 h	+/- 24 h	-4h	+ 10 min	+/- 1 h	-4h	+ 10 min	-4h	+ 10 min	-4h	+ 10 min	+/- 1 h	+/- 24 h	-4h	+ 10 min	
8.5	PK Sample		x	x	x	x	x	x	x	x	x	x	x	x	x	x	x	x	x	x
8.6	ADA		x				x			x		x		x				C7 and then every 3 cycles		x
8.8.1	PD Serum		x				x			x				x				At the time of tumor assessment		x
	PD Plasma		x				x			x				x				C9 and then every 3 cycles		x
	Whole Blood Flow Cytometry		x			x	x			x				x			x	C9 and then every 3 cycles		x
	Whole Blood RNA		x							x										
	bTMB/ctDNA		x				x			x										
8.7.1	WGS		x																	
8.8.1	Archival Tumor Sample	x																		
8.8.2	Fresh Tumor Biopsy (Optional ^b)	x								x (+2/-1 day[s])										
	Tongue Scrape (Optional ^c)		x (+0/-5 day[s])									x (+0/-5 day[s])								
	Stool Sample (Optional ^c)		x (+0/-5 day[s])									x (+0/-5 day[s])								
8.9	RBR Sample (Saliva DNA) Optional ^d		x																	

Table 2 Hourly Schedule of Assessments (cont.)

Abbreviations: ADA = Anti-drug antibody; C = Cycle; EOI = End of infusion; h = Hour; PD = Pharmacodynamic; PK = Pharmacokinetic; Q2W = Every two weeks; RBR = Research biosample repository; WGS = Whole genome sequencing.

- a) Assessments (e.g., pre-dose) should be performed relative to the start of the study drug infusion except for those at EOI time-points.

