	as measured by the European Organisation for Research and Treatment of Cancer (EORTC) Quality-of-life questionnaire (QLQ)-C30, IL97, and OES-18, defined as an improvement of at least 10 points
To investigate the pharmacokinetics (PK) of RO7247669 and nivolumab.	
 Serum concentrations, PK profiles and parameters for RO7121661, RO7247669, and nivolumab
To evaluate the immune response after administration of RO7247669 and nivolumab.	
 Incidence and titer of RO7121661, RO7247669 or nivolumab anti-drug antibodies (ADAs) during the study relative to the prevalence of ADA at baseline
To assess treatment-induced pharmacodynamic changes (PD Biomarkers) in peripheral blood and tumor microenvironment	
 Changes from baseline in the phenotype and activation status (CD4/CD8 HLA-DR+Ki67+) of T-cell subsets in the peripheral blood Changes from baseline such as CD8 T-cell infiltration, proliferation (CD8+Ki67+) in the tumor microenvironment
To assess baseline characteristics in the tumor microenvironment as predictive biomarkers of response	
 Baseline PDL1, CD8+PD1+, CD8+TIM3+, and CD8+LAG3+ expression in the tumor microenvironment
Exploratory	
To evaluate the efficacy of RO7121661 and RO7247669 compared with nivolumab.	
 Changes in disease-related symptoms, function, and health-related quality of life as measured by the EORTC QLQ-C30, IL-97, and OES-18 Proportion of responses on the PGI-CI and PGI-S
To evaluate the efficacy of RO7121661 compared with nivolumab.	
 OS, defined as the time from randomization to death from any cause ORR, DCR, DoR, PFS as defined above according to RECIST v1.1 Proportion of participants reporting clinically meaningful improvement in global health status/quality of life, emotional functioning, social functioning and dysphagia as measured by the EORTC QLQ-C30, IL97, and OES-18, defined as an improvement of at least 10 points
To investigate the PK of RO7121661	
 Serum concentrations, PK profiles and parameters for RO7121661.
To evaluate the immune response after administration of RO7121661	
 Incidence and titer of RO7121661 ADAs during the study relative to the prevalence of ADA at baseline

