4.2 JUSTIFICATION FOR RO7121661 DOSE AND SCHEDULE

A fixed dosing regimen of 2100 mg Q2W was selected as the dose for this study for RO7121661. [REDACTED]

[REDACTED] During the dose-escalation in Part A of the study, no specific safety concern associated with RO7121661 was identified. In total, one single DLT (Grade 3 TnT increased) was reported and observed at the highest 1200-mg dose group, and no MTD was reached. Anti-tumor activity, as measured by radiographic PRs, was observed at the selected dose for this study. A two compartmental PK linear model predicts the exposure data well, particularly at the higher dose range. A dose regimen of 2100 mg Q2W is predicted to result in a trough concentration of > 320 µg/mL, the predicted EC95 from an ex vivo SEB cytokine assay, in 62% of participants.

In addition, RO7121661 was well tolerated in both the dose-range finding and GLP monkey toxicology studies up to the highest dose evaluated (150 mg/kg). Toxicology findings were consistent with reported findings in cynomolgus monkey studies with marketed CPIs.

Supporting data for the selected dose can be found in the [RO7121661 Investigator's Brochure](#).

[REDACTED]

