8.6 IMMUNOGENICITY ASSESSMENTS

As the study drugs are human antibodies, there is a risk that ADAs against the study drugs could develop, potentially reducing their efficacy and/or potentially resulting in symptomatic hypersensitivity reaction, including immune-complex reactions.

Antibodies to the study drugs will be evaluated in blood samples collected from all participants according to the SoAs (Section 1.3). For each collected ADA sample, a corresponding PK sample will be collected at the same time-point for the determination of the study drug concentration. During the course of the study, ADA sampling time-points may be modified based on emerging data to ensure the immunogenicity of RO7121661 and RO7247669 can be adequately characterized.

Validated screening, confirmatory, and titer assays will be employed to detect ADAs. The date and time of each sample will be recorded in the eCRF.

If required, remaining volumes of ADA samples may also be used for assay development/validation experiments, ADA characterization, for compound-related exploratory analyses, or to help develop further blood tests, after they are used for the mentioned intended uses.

The blood samples will be destroyed within 2 years after the date of final clinical study report, or earlier, depending on local regulations unless participants give optional consent for further use of remaining samples as part of RBR after the end of the study.

Details on sampling procedures, sample storage, and shipment are documented in the sample documentation.

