8.11.3 Assessments at Treatment Discontinuation Visit

Participants who discontinue study treatment early will be asked to return to the clinic ≤ 30 days after the final dose of study drug for a follow-up visit. The visit at which response assessment shows progressive disease may be used as the treatment discontinuation visit.

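### ADA incidence is promised for a follow-up period in which no ADA sample is scheduled, and the ADA-negative rule ignores the paired drug level

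*Combined protocol and SAP*

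**What the plan says.** The secondary immunogenicity endpoint in Section 3 (Table 5) is the incidence and titer of "anti-drug antibodies (ADAs) during the study relative to the prevalence of ADA at baseline". Section 9.3.5 turns this into a baseline prevalence and a "post-baseline incidence during both the treatment and follow-up periods".

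For timing, Table 1 in Section 1.3 only points onward: "Refer to Hourly Schedule of Assessments for specific sample collection timepoint details". Table 2 then places ADA samples before dosing in Cycles 1 to 5, at "C7 and then every 3 cycles", and once at treatment discontinuation. That last visit falls within 30 days of the final dose. Section 8.11.3 lets it come earlier: "The visit at which response assessment shows progressive disease may be used as the treatment discontinuation visit".

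For classification, Section 9.3.5 states: "Participants are considered to be ADA negative if they are ADA negative at baseline and all post-baseline samples are negative". No condition on drug level is attached, and there is no inconclusive category. Section 8.6 nevertheless provides the data for one: "For each collected ADA sample, a corresponding PK sample will be collected at the same time-point for the determination of the study drug concentration".

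**The concern.** Two things do not fit together. The analysis names a period for which the schedule collects no ADA data. The negative rule also treats every negative reading as equally informative, although drug in the sample can mask ADA and the measurement that would show this is already being taken.

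Immunogenicity of RO7247669 and nivolumab is a secondary objective, and Section 9.3.3 has ADA results summarised by arm. If drug levels exceed an assay's tolerance, unreadable negatives are counted as true negatives. With doses of 2100 mg and 240 mg, the extent of this could differ between the arms. The same participants would also enter the ADA-negative group in the ADA-status summaries for safety, efficacy, PK and biomarkers (Sections 9.2 and 9.3.5).

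**Working it through.** The protocol gives no ADA rate, assay tolerance or ADA precision target, so there is no figure of its own to reproduce.

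**Window against schedule**

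- Section 9.3.5 covers the treatment and follow-up periods.
- Table 1 has separate columns for treatment discontinuation (within 30 days of the last dose) and follow-up (day 90 ± 7, then every 3 months).
- Table 2 has a treatment discontinuation column with an ADA sample, and no follow-up column.
- Section 8.11.4 has follow-up collecting survival status, new therapies and PROs, with contact allowed by phone or from records. No blood draw is described.

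No scheduled sample therefore falls in the follow-up period.

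**Could drug level matter, and differently by arm?**

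Inputs from the documents: 2100 mg and 240 mg, both every two weeks (Section 4.1), and a predicted trough above 320 µg/mL for RO7121661 (Section 4.2). Assumptions not in the documents: a trough of exactly 320 µg/mL at day 14 for either 2100 mg drug, dose-proportional levels, the same kinetics in all arms, and a half-life h of 7 to 25 days.

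- Dose ratio: 2100/240 = 8.75. Scaled 240 mg trough: 320/8.75 = 36.6 µg/mL.
- Level at day t after the last dose: C(t) = C(14) × 0.5^((t − 14)/h).

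| | Day 14 | Day 30 (latest scheduled ADA sample) | Day 90 (follow-up starts) |
|---|---|---|---|
| 2100 mg, h = 7 | 320 | 65.6 | 0.2 |
| 2100 mg, h = 25 | 320 | 205.3 | 38.9 |
| 240 mg, h = 7 | 36.6 | 7.5 | 0.0 |
| 240 mg, h = 25 | 36.6 | 23.5 | 4.4 |

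- Tolerance of 50 µg/mL for both assays (assumed): exceeded at 2100 mg on days 14 and 30 but not on day 90, and never at 240 mg.
- Tolerance of 400 µg/mL for both (assumed): exceeded in neither arm.
- Direction: what counts is level divided by tolerance. The 2100 mg to 240 mg ratio of that quantity is 8.75 × (nivolumab assay tolerance / RO7247669 assay tolerance). If the RO7247669 assay tolerates more than 8.75 times as much drug as the nivolumab assay, nivolumab becomes the arm more open to masking.

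**Effect within one arm**

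Reported incidence = true incidence × (1 − masked share). With an assumed true incidence of 20%, masked shares of 0, 25, 50 and 75% give 20, 15, 10 and 5%. The masked share cannot be derived from the documents for any arm.

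**Effect of excluding inconclusive participants**

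Suppose 20 of 100 participants are truly positive and all are detected, and half of the 80 negatives are excluded. Incidence then reads 20/(20 + 40) = 33% instead of 20%. Exclusion can overstate incidence, so it should not be the main figure.

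**The case against.** On the window, the sponsor can say that Section 8.11.3 itself describes the discontinuation visit as a follow-up visit, that Section 8.6 allows ADA time-points to be changed, and that Section 8.11.5 allows unscheduled samples when clinically indicated. These soften the point but do not remove it. Table 1 separates the two periods, and no ADA sample is specified from day 90 onward.

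On masking, four objections stand.

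- A reader might infer that every post-baseline sample is taken with substantial drug present. Section 7.1.2 allows suspensions of up to 12 weeks, with cycles delayed and not skipped. On the assumed 320 µg/mL trough and half-lives of 10 to 25 days, a further 84 days leaves 320 × 0.5^(84/10) ≈ 1 to 320 × 0.5^(84/25) ≈ 31 µg/mL. Cycle 2 pre-dose also follows only one dose.
- A reader might take the 62% in Section 4.2 as the share of RO7247669 participants whose ADA would be masked. The protocol attaches it to "the predicted EC95 from an ex vivo SEB cytokine assay, in 62% of participants". That is a pharmacological target for RO7121661. It is not an ADA drug tolerance, and it does not describe RO7247669.
- A reader might infer from the doses that the error favours the experimental drug. Tolerances are not given and may differ between assays, so the dose ratio does not settle the direction.
- The immunogenicity objective is not worded as a comparison with nivolumab, and no test or decision uses ADA.

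The sponsor may also handle drug tolerance in the separate statistical document announced in Section 9.3, which is not among the documents reviewed. That remains possible, but the rule written in Section 9.3.5 would count an uninterpretable negative as a true one.

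**Conclusion.** Both textual points hold. ADA incidence in the follow-up period cannot be reported from the planned samples, and ADA-negative status is assigned without regard to the paired drug concentration. Under-detection that differs between 2100 mg and 240 mg is possible. Its existence, size and direction depend on each assay's drug tolerance and on actual drug levels, neither of which the documents give. The illustrative levels rest on assumed half-lives and dose proportionality, and on a trough borrowed from RO7121661. They range from a problem confined to the 2100 mg arms to none at all, so no bias in favour of RO7247669 is shown. Because every ADA analysis is descriptive, severity is low. The change is still worth making because the data it needs are already planned.

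**What to change.** 1. Restate the Section 9.3.5 window as first dose to the treatment discontinuation visit.
2. Use the paired PK sample to flag each negative post-baseline ADA sample whose drug level is above that assay's validated tolerance. Among participants with no positive sample, report by arm as *ADA inconclusive* those whose negatives are all above tolerance, or whose within-tolerance negatives are only early ones (for example Cycle 2 pre-dose). Define early before unblinding, since one early low-drug sample should not certify a participant as negative for the whole study.
3. Keep incidence with inconclusive participants counted as negative as the main figure. Show incidence with them excluded as a sensitivity analysis, with a note that exclusion can overstate it. Repeat the ADA-status subgroup summaries without them.
4. State each assay's drug tolerance beside the incidence for its arm.

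The cost is wording and some programming, using PK samples already scheduled and tolerance figures from assay validation. The downside is a smaller ADA-evaluable denominator in the sensitivity analysis. If follow-up incidence is truly wanted, a paired ADA and PK sample at the day-90 visit would be needed instead. That adds a blood draw to a contact that may now be made by phone.
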